proinflammatory cytokines (tumor necrosis factor [TNF], IL-6, and IL-1 β) that likely drive inflammation and thrombophilia, which leads to clot formation, in these patients. In doing so, we hypothesize that TPE will lead to improved clinical outcomes in critically ill COVID-19 patients compared to those receiving standard of care (SOC).

Primary Objectives

1. Evaluate change in plasma viscosity after TPE vs SOC in critically ill COVID-19 patients.
2. Evaluate safety and tolerability of TPE vs SOC in critically ill COVID-19 patients.

Secondary Objectives

Compare outcomes of TPE vs SOC for the following measures:

1. Mortality
2. Bleeding/thromboembolic complications
3. Requirement for major forms of supportive care (mechanical ventilation, RRT, etc.)
4. Time to treatment failure
5. Duration of ICU stay
6. Total time to hospital discharge
7. Clinical and laboratory evaluation, by system

3. Background

The COVID-19 pandemic caused by the SARS-CoV-2 virus can cause a spectrum of disease ranging from asymptomatic/mild pneumonia in 80% of patients, to critical illness (respiratory failure, septic shock and/or multiple organ dysfunction/failure) in 5% of patients³. However, it has been a challenge to decipher the cause of severe COVID-19-related complications and therefore define optimal approaches to treat critically ill patients with COVID-19, particularly those with signs of severe organ injury that often develop multi-organ failure.

In a preliminary study analyzing various laboratory markers in COVID-19 patients that may contribute to inadequate blood flow and therefore compromised organ function, we observed elevated plasma viscosity measurements ranging from 1.9-4.2 centipoise (cp, normal range is 1.4-1.8 cp) in 15 critically ill patients⁴. These results suggest that altered blood flow secondary to hyperviscosity may directly alter blood flow, contributing to end organ injury and possibly death. In these cases of severe COVID-19, hyperviscosity was strongly correlated with higher Sequential Organ Failure Assessment (SOFA) scores, a measure of mortality risk and level of organ dysfunction in ICU patients (Pearson $r = 0.841$, $R^2 = 0.7072$, $p < 0.001$)⁴.

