plasma viscosity > 3.5 cp or if clinical condition worsens to a point that warrants TPE as salvage therapy based on best clinical judgment of ICU team, participants will be considered to be in treatment failure and offered additional TPE as part of their SOC. Patients in whom this happens will still be followed for outcome measurements.

In the SOC arm, participants will not receive TPE with FP, but continue to receive SOC and be closely monitored by ICU team for any change in clinical status. Plasma viscosity will be measured on Day 1 and Day 3. Additional laboratory parameters will be acquired in parallel as per standard management. Medical records of the study participants will be reviewed to obtain clinical data including physician records, hospital records, clinical records, and laboratory results. At any point during study period, if plasma viscosity > 3.5 cp or if clinical condition worsens to a point that warrants TPE as salvage therapy based on best clinical judgment of ICU team, participants will be considered as treatment failure and offered TPE as part of their SOC. Patients in whom this happens will still be followed for outcome measurements.

7. Data and Specimen Banking

Discarded clinical specimens collected as part of routine clinical care of participants during study period, along with discarded apheresed patient plasma, will be collected and stored in PI's laboratory for future research studies. These include discarded clinical specimens prior to and after each TPE treatment, but no additional specimens will be collected for non-clinical research purposes only. Data will be deidentified and coded to remove identifying information. An electronic key linking the patient identifiers with the sample ID will be maintained on access-restricted Emory server and restricted to the study PI and co-investigators.

8. Sharing of Results with Participants

Clinical data will be entered into patient medical records, and study participants will be able to request them through the medical records office at their respective hospital. Study results will be made available as publication.

9. Study Timelines

- The duration of an individual participant's participation in the study is for the duration of their hospitalization.
- The duration anticipated to enroll all study participants:

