This trial will provide important estimates of variability (within-subject and between-subject standard deviation) for plasma viscosity. The estimates of variability will be valuable to power future clinical trials since these variability estimates are essential components for sample size calculations. Due to the small sample sizes, results from these studies will also focus on the magnitude of the differences for each outcome, consistency of findings and clinical significance.

Duration of ICU stay, total time to hospital discharge and time on respiratory support will be compared by treatment group with the Wilcoxon rank-sum test. The assessment for a difference in hospital mortality and bleeding/thromboembolic complications by treatment group will be a two-sided exact chi-square test.

Study Ability to Detect Uncommon Safety Events

Adverse Events (AE) means any untoward medical occurrence associated with the use of an intervention in humans, whether or not considered intervention-related (21 CFR 312.32 (a)). An adverse event (AE) or suspected adverse reaction is considered "serious" if, in the view of either the investigator or sponsor, it results in any of the following outcomes: death, a life-threatening

adverse event, inpatient hospitalization or prolongation of existing hospitalization, a persistent or significant incapacity or substantial disruption of the ability to conduct normal life functions, or a congenital anomaly/birth defect. The following guidelines will be used to describe severity.

- **Mild** – Events require minimal or no treatment and do not interfere with the participant's daily activities.
- **Moderate** – Events result in a low level of inconvenience or concern with the therapeutic measures. Moderate events may cause some interference with functioning.
- **Severe** – Events interrupt a participant's usual daily activity and may require systemic drug therapy or other treatment. Severe events are usually potentially life-threatening or incapacitating. Of note, the term "severe" does not necessarily equate to "serious".]

All adverse events (AEs) must have their relationship to study intervention assessed by the clinician who examines and evaluates the participant based on temporal relationship and his/her clinical judgment. The degree of certainty about causality will be graded using the categories below.

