- **Related** – The AE is known to occur with the study intervention, there is a reasonable possibility that the study intervention caused the AE, or there is a temporal relationship between the study intervention and event. Reasonable possibility means that there is evidence to suggest a causal relationship between the study intervention and the AE.
- **Not Related** – There is not a reasonable possibility that the administration of the study intervention caused the event, there is no temporal relationship between the study intervention and event onset, or an alternate etiology has been established.

All participants in this study are critically ill with COVID-19 and require ICU admission. Such patients experience frequent complications and events that can cause deterioration in function of any and all vital organs. Any medical condition that is present at the time that the participant is screened will be considered as baseline and not reported as an AE. However, if the study participant's condition appears to deteriorate in response to the procedure it will be recorded as an AE.

The table below addresses safety using adverse event probabilities based on the targeted enrollment of 10 patients in each treatment group. The table provides the binomial probabilities of observing 0, 1+, or 2 or more occurrences of an AE during follow-up.

Adverse Event Probabilities for n=10 PLEX patients or n=10 standard of care patients

Event Rate (AE)	Probability [0 / 10 Events]	Probability [1+ / 10 Events]	Probability [2+ / 10 Events]
5%	0.60	0.40	0.09
10%	0.35	0.65	0.26
15%	0.20	0.80	0.46

Thus, we can be **80%** sure of observing at least one episode of a rare AE if the true rate of an AE is 15%.

Adverse Events and Laboratory Toxicities: Each adverse event and each laboratory toxicity will be counted only once per participant as the most severe level reported during follow-up. Tabular summaries of the number of participants reporting each AE, for both treatment-related and unrelated AEs as well as just treatment related AEs, respectively will be reported. Adverse events and grade III or higher laboratory toxicities observed during follow-up will be reported by treatment group.

Data Storage

1. All data will be kept on encrypted and password-secure Emory University Hospital computer systems, encrypted devices that are Emory IT vetted, or secure Emory servers, such as Trusted storage, with only the investigators listed having access to review the data.

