All AEs including local and systemic reactions not meeting the criteria for SAEs will be captured on the appropriate case report form (CRF). Information to be collected includes event description, time of onset, clinician's assessment of severity, relationship to study product (assessed only by those with the training and authority to make a diagnosis), and time of resolution/stabilization of the event. All AEs occurring while on study must be documented appropriately regardless of relationship. All AEs will be followed to adequate resolution.

Changes in the severity of an AE will be documented to allow an assessment of the duration of the event at each level of severity to be performed. AEs characterized as intermittent require documentation of onset and duration of each episode.

19. Provisions to Protect the Privacy Interests of Participants

- The research team will take steps to make the participants feel at ease with the research situation in terms of the questions being asked and the procedures being performed.
- The participants will be reassured that no private data will be shared with anyone outside the study and that they have the right to withdraw without fear of penalty at any time prior to, during, or after enrollment.
- The participants will be given an opportunity to ask any questions or address any concerns they may have at the time of recruitment or anytime thereafter.
- The research team is permitted to access clinical information from the participant's electronic medical record for data analysis.

20. Economic Burden to Participants

There are no costs that participants will be responsible for because of participation in the research.

21. Consent Process

Consent for study enrollment will be carried out by study co-investigators that are part of the clinical care team. The consent discussion should take approximately ten minutes; however, the discussion will continue as long as is necessary to answer all of the patient's questions. We will minimize coercion or undue influence by emphasizing that the patient has the choice to decline participation and will not be compensated for their time or effort. In order to ensure that the patient understands the process, we will provide time for follow up questions. Consent will be obtained in English, but an

appropriate medical interpreter will be used if the prospective participants do not understand and/or speak English.

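### Worsening of a condition present at screening becomes an AE, by the only stated route, through the procedure that only the TPE arm is assigned, so by-arm AE tables are not comparable for pre-existing conditions

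*Combined protocol and SAP*

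**What the plan says.** Two consecutive sentences in Section 17 (Study Ability to Detect Uncommon Safety Events) set the rule. The first excludes: "Any medical condition that is present at the time that the participant is screened will be considered as baseline and not reported as an AE". The second opens with a word of contrast and lets one kind of event back in: "if the study participant's condition appears to deteriorate in response to the procedure it will be recorded as an AE". No other sentence says how worsening of a baseline condition is to be handled.

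Other parts of the protocol are broader:

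- Section 17 defines an AE as "any untoward medical occurrence associated with the use of an intervention in humans, whether or not considered intervention-related".
- Section 17 plans participant counts for each AE, once for related and unrelated events together and once for related events alone, with AEs reported by treatment group.
- Section 18 has AEs collected on every participant and adds: "All AEs occurring while on study must be documented appropriately regardless of relationship".
- Section 2 makes safety a primary objective in comparative form: "Evaluate safety and tolerability of TPE vs SOC in critically ill COVID-19 patients".

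On exposure, Section 6 says: "In the SOC arm, participants will not receive TPE with FP, but continue to receive SOC". If SOC fails, "participants will be considered as treatment failure and offered TPE as part of their SOC".

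**The concern.** Everyone enrolled is already critically ill in an ICU, and Section 17 says of them: "Such patients experience frequent complications and events that can cause deterioration in function of any and all vital organs". A good part of what goes wrong after randomization will therefore be worsening of something already present, such as shock or poor oxygenation. For exactly that class of event, the entry test is whether the decline appears to be a response to TPE. Causal attribution, which should be a field completed after an event is recorded, instead decides whether it is recorded.

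This has two consequences. Between arms, an SOC patient with no TPE exposure cannot meet the test, while a TPE patient with the same decline can. Within the TPE arm, worsening that nobody attributes to TPE has no stated route into the AE record. No blinding of AE assessment is described, and the examining clinician makes the judgment.

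At stake are the by-arm AE tables and, through them, the comparative safety objective and the principal investigator's continuing review under Section 18 of whether safety favors continuation.

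**Working it through.** **1. The plan's own safety figures.** Section 17 gives binomial probabilities for 10 patients per arm. At a true rate of 15%:

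- P(0 events) = 0.85^10 = 0.197
- P(1 or more) = 1 − 0.197 = 0.803
- P(2 or more) = 1 − 0.197 − 10 × 0.15 × 0.85^9 = 0.456

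The plan states 0.20, 0.80 and 0.46. The 5% row (0.599, 0.401, 0.086) and the 10% row (0.349, 0.651, 0.264) also agree. The table is correct. It is offered for either arm, so it presumes that an event in an SOC patient can be recorded.

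**2. Event types against the text.**

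| Event after screening | TPE patient | SOC patient, no TPE | SOC patient, after salvage TPE |
|---|---|---|---|
| New condition | AE | AE | AE |
| Baseline condition worsens, judged a response to the procedure | AE | cannot arise | AE |
| Baseline condition worsens, not so judged | no stated route | no stated route | no stated route |

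The second row is open to one arm by assignment. The third row is where Section 17's AE definition would record the event and the baseline rule does not. Section 18's instructions do not settle this, because they govern events that already count as AEs. The planned count of unrelated AEs would also miss the third row.

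**3. Illustration on assumed rates.** The documents give no worsening, attribution or salvage rate. Let w be the true proportion whose baseline condition worsens (the same in both arms), a the share of TPE-exposed worsening attributed to TPE, and s the share of SOC patients given salvage TPE. Followed as written:

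- recorded in the TPE arm = w × a
- recorded in the SOC arm = w × a × s

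With w = 0.50 and s = 0:

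| a | TPE recorded | SOC recorded | False gap | TPE worsening not recorded |
|---|---|---|---|---|
| 0.10 | 5% | 0% | 5 points | 45 points |
| 0.30 | 15% | 0% | 15 points | 35 points |
| 0.50 | 25% | 0% | 25 points | 25 points |

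With w = 0.50, a = 0.30 and s = 0.20, SOC records 0.50 × 0.30 × 0.20 = 3%, and the gap is 12 points.

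**4. Effect on the 80% statement for the SOC arm.** Take w = 0.15 and a = 1. The chance of recording at least one worsening event among 10 SOC patients is 1 − (1 − 0.15 × s)^10:

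- s = 0: 0
- s = 0.20: 1 − 0.97^10 = 0.26
- s = 0.40: 1 − 0.94^10 = 0.46

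A symmetric rule gives 0.80, as tabulated. The figures for s above zero are generous to the plan, because worsening that leads to salvage TPE comes before it and cannot be a response to it.

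**The case against.** The strongest reply is that the text never says other deterioration will not be recorded. The exception sentence could refer to the patient's overall state and simply make sure that procedure-linked decline is always captured, leaving the broad definition and Section 18 to cover the rest. That reading is possible, and part of it stands: the exclusivity is inferred from a single stated exception. But the exclusion sentence is explicit, the next sentence is framed as the contrast to it, and nothing else brings worsening back in. Staff following one section and staff following the other would complete the CRF differently.

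Several stronger conclusions that a reader might draw are not supported:

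- *The SOC rate for pre-existing conditions is fixed at zero.* It is not, because SOC patients may receive salvage TPE.
- *Transfusion reactions such as TRALI or TACO would be lost as baseline.* They are new events, not conditions present at screening. Section 15 lists them, and Section 18 requires related events on that list to reach the principal investigator within 24 hours. Misattribution remains possible, but a symmetric recording rule would not remove it.
- *The trial cannot address its safety objective.* Section 4 follows the ordinal scale, SOFA, PaO2/FiO2, ventilatory ratio, vasopressor need and RRT. Mortality and bleeding/thromboembolic complications are tested by arm, and grade III or higher laboratory toxicities are reported by arm. Much of the worsening is therefore visible, though not labelled as an AE.
- *The primary safety endpoint is distorted by the missing unattributed events.* It counts only AEs directly associated with TPE, so unattributed worsening would not enter it under any recording rule.

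AE reporting is tabular with no planned test, so the consequence is a misleading comparison and not an inflated type I error.

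**Conclusion.** The concern holds in a limited form. For conditions present at screening, the stated rule makes causal attribution the condition for recording, and only one arm meets the exposure condition by assignment. It conflicts with the AE definition in the same section and sits badly with Section 18. If it is followed as written, the by-arm AE tables are not comparable for this class of event: a false excess under TPE where worsening is attributed, and an under-count where it is not.

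The size cannot be computed from the documents. The 15% against 0% contrast rests on three assumptions (50% true worsening in both arms, 30% attribution, no salvage TPE) and on reading the exception as the sole route. Events outside that class, and the outcomes collected separately, are not touched.

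**What to change.** Replace the exception sentence in Section 17 with a symmetric rule, for example: *A condition present at screening is recorded as an AE if it worsens in severity from its baseline level after randomization, in either arm, over the same observation window and whatever the suspected cause; relationship to TPE is assessed afterwards.* Then reconcile the baseline paragraph with the AE definition in Section 17 and the collection instructions in Section 18. The relatedness field already in the CRF content (Section 18) can feed the treatment-related table unchanged.

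The cost is more AE entries in a 20-patient ICU trial, plus one definition. The CRF must state what counts as worsening from baseline, because the Section 17 severity grades rest largely on interference with daily activities and separate ICU patients poorly. Without a threshold, routine fluctuation would be recorded as AEs. The change alters no treatment. It is best made before data are collected, since the grade and timing of unrecorded worsening may be hard to reconstruct from records.
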